9.5 Secondary Endpoints

 Adverse events will be mapped to a primary MedDRA System Organ Class (SOC) and Preferred Term (PT). Anticipated AEs and SAEs and unanticipated AEs and SAEs will be summarized during each Evaluable Period by SOC and PT. In addition, all devicerelated AEs and SAEs will be summarized during each Evaluable Period by SOC and PT.

An overview of the total number of AEs and SAEs (anticipated, unanticipated, and device-related) during each Evaluable Period will be provided. In addition, for each Evaluable Period an overview will be provided of the total number of subjects having at least 1:

- Anticipated AE
- Anticipated SAE
- Unanticipated AE
- Unanticipated SAE
- Device-related AE
- Device-related SAE

The proportion of subjects having at least one AE within each of these six AE subgroups will be compared between Evaluable Periods with exact McNemar's tests. For each of these six AE subgroups the hypotheses will be:

$$H_0: P_u = P_a$$

 $H_a: P_u \neq P_a$

Where P_u = Proportion of subject having at least 1 event during unassisted treatments and P_a is the proportion of subjects having at least 1 event during the Assisted treatments.

Identifying the number of subjects who had at least 1 event during assisted treatment and no event during unassisted treatment as n_{12} , and subjects who have no event during assisted treatment and at least 1 event during unassisted treatment as n_{21} , the indicator

$$Q = \frac{(n_{12} - n_{21})^2}{(n_{12} + n_{21})}$$
 will be compared to x^2 with 1 Degree of Freedom if

$$(n_{12} + n_{21}) > 20$$
. Otherwise the correction $Q = \frac{(|n_{12} - n_{21}| - 1)^2}{(n_{12} + n_{21})}$ will

be used. The Null Hypothesis will be rejected if the P-value for the x^2 is less than 0.10.

No multiplicity adjustment will be done for these secondary endpoints.

Furthermore, the proportion of subjects having AEs within each of these six AE subgroups will be summarized by SOC, PT and severity (mild, moderate or severe) during each Evaluable Period for the most severe rating of each AE per subject.

 The incidence of decreased serum phosphorus defined as at least 1 post-dialysis serum phosphorus level < 2.2 mg/dL, the incidence of elevated serum phosphorous defined as a least 1 post-dialysis serum phosphorus level > 5.5 mg/dL, will each be compared between Evaluable Periods with exact McNemar's tests.

- 3. The incidence of decreased serum potassium defined as at least 1 post-dialysis serum potassium level of < 3.5 meq/L, and the incidence of elevated serum potassium defined as at least 1 post-dialysis serum potassium level of > 5.9 meq/L, will each be compared between Evaluable Periods with exact McNemar's tests.
- A descriptive summary of UF and target weight during each evaluable period will be provided.

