The Unassisted Home Evaluable Period will conclude after a minimum of 34 treatments (5-10 hours in length). If the subject successfully completes the study, seamless enrollment into the Extension Study (DKPL-00674-001: An Open Label Study to Allow Patients Continuous Use of the HemoCareTM Hemodialysis System for Home Hemodialysis Prior to Market Authorization) is possible, for continued access to the device. If the subject elects not to enroll in the Extension Study, or does not successfully complete the study, the subject will resume HD therapy on another device as prescribed by their regular physician.

4 Objectives and Endpoints

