4.1 Objectives

4.1.1 Primary Objectives

Safety

To compare the safety of HemoCare™ Hemodialysis System, as measured by adverse events, between the Assisted and Unassisted Home Evaluable Periods.

Performance

To compare the performance of HemoCareTM Hemodialysis System, as measured by dialysis adequacy (weekly stdKt/V_{urea}), between the Assisted and Unassisted Home Evaluable Periods

4.1.2 Secondary Objectives:

- To compare descriptively all reported adverse events (AE) and serious adverse events (SAE; anticipated, unanticipated, and device-related) between the Assisted and Unassisted Home Evaluable Periods.
- 2. To assess the safety of the treatment, as measured by control of serum phosphorus levels, during the Assisted and Unassisted Home Evaluable Periods.

- 3. To assess the safety of the treatment, as measured by control of serum potassium levels, during the Assisted and Unassisted Home Evaluable Periods.
- 4. To evaluate UF data within and between the Assisted and Unassisted Home Evaluable Periods, as assessed by the difference between the fluid weight removed as measured by the device and the subject's weight change as measured by a scale.

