 - Note: Subjects may exit the Assisted Evaluable Period before training is complete if all required treatments have been performed. Treatment of these subjects will continue to be administered by a medical professional in Transition B Period until such time that clinical staff is able to affirm subject and care partner training and capability to safely perform independent nocturnal HD treatments.
- Installation of HemoCare™ Hemodialysis System into the subject's home will be targeted during this period if it has not occurred earlier.

7.1.5 Assisted Evaluable Period Visit 1

On-site visit will be conducted at Week 3 of the Assisted Evaluable period. The following assessments will be performed:

- Physical Exam
- Vital signs
- Adverse Events/Serious Adverse Events assessment and confirmation
- Concomitant medications
- Care Plan review and prescription adjustment, if needed.

Additional procedures might be performed based on the Investigator's judgment.

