9.1 General Considerations

Further details of the planned statistical methods presented below will be provided in the study statistical analysis plan (SAP). The purpose of the SAP is to further elaborate the statistical methods described in the protocol and describe analysis conventions to guide the statistical programming work. Any changes to the final SAP will be documented. Unless otherwise specified, treatment effects will be evaluated based on a 2-sided significance level of 0.050 (when rounded to 3 decimal places)

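### Section 9.5 tests subjects with at least one event or abnormal value without regard to treatments received or samples taken and without an interval, so early leavers can flatter the Unassisted period and non-rejection is weak evidence

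*Combined protocol and SAP*

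**What the plan says.** Section 9.5 forms six categories (anticipated, unanticipated and device-related, each for AEs and SAEs) and counts subjects with at least one event in each period: "The proportion of subjects having at least one AE within each of these six AE subgroups will be compared between Evaluable Periods". The same sentence names the test: "AE subgroups will be compared between Evaluable Periods with exact McNemar's tests"; the null hypothesis is "rejected if the P-value for the x^2 is less than 0.10". Items 2 and 3 do the same for post-dialysis phosphorus and potassium; high potassium, for example, is "defined as at least 1 post-dialysis serum potassium level of > 5.9 meq/L". No level is given for the laboratory tests, so the default in section 9.1 would apply: "treatment effects will be evaluated based on a 2-sided significance level of 0.050". The section states no interval, exposure term or population.

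The primary analyses differ. Section 9.4.1 models total AEs with a log-treatments offset and a 90% CI for the rate ratio, and section 9.4.2 gives a 90% CI for its difference in proportions.

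Period length is a minimum, with no maximum stated: "The Unassisted Home Evaluable Period will conclude after a minimum of 34 treatments" (section 3.3). Pre- and post-dialysis phosphorus and potassium are drawn monthly in both Evaluable Periods (Table 2, note 4). The matching secondary objective in section 4.1.2 is worded "To compare descriptively all reported adverse events (AE) and serious adverse events".

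**The concern.** The chance of at least one event rises with the number of treatments, and the chance of at least one abnormal value rises with the number of samples. McNemar's test sees only yes or no per period. A subject who stops part-way through the Unassisted period has less opportunity for an event there and can enter the table as event-free. Section 9.5 does not say how such a subject, or one who never reaches that period, is handled.

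This matters because section 9.2 rests the safety determination on a clinical reading of how often AEs occur and of what type, naming device-relatedness. The exposure-adjusted model covers only all AEs together. The device-related, serious and unanticipated categories are formally compared only through the unadjusted tests. With about 30 pairs and no interval, a reader has nothing to show how large a difference remains compatible with a non-significant result.

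**Working it through.** **Inputs from the plan.** At least 30 subjects and 34 treatments per period at 3.5 per week (section 9.2); two-sided 0.10 for the AE tests (9.5); default 0.050 (9.1); monthly samples (Table 2). The plan's own exposure figure reproduces: 30 × 34 = 1020 treatments per period, against a target of at least 1000. Period length is 34 / 3.5 = 9.7 weeks, or 68 days, which holds 2 or 3 monthly samples.

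**Assumptions.** The documents give no event rate, abnormal-value rate or exposure ratio. I take 0.1 to 1.0 events per 34 treatments, Poisson events, independent periods and samples within subject, and 10 or 20% abnormal per sample. Rejection probabilities are exact enumerations with 30 pairs.

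**1. Exposure and the at-least-one proportion.** P = 1 − exp(−expected events).
- At 0.5 events per 34 treatments, P = 39.3%. If the Unassisted rate is doubled but only half the treatments are received, expected events are again 0.5 and P is again 39.3%: the doubling disappears.
- If 6 of 30 subjects leave before the Unassisted period and are counted as event-free, 39.3% appears as 0.8 × 39.3% = about 31%.
- With equal true rates and one period 1.25 times as long, false rejection at 0.10 is 3.6 to 11.2%, so a modest imbalance among completers does little harm.

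**2. Number of laboratory samples.** P = 1 − (1 − q)^k.

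| q per sample | k = 2 | k = 3 |
|---|---|---|
| 10% | 19.0% | 27.1% |
| 20% | 36.0% | 48.8% |

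If every subject had 2 samples in one period and 3 in the other, false rejection would be 6 to 11% at the 0.05 default and 11 to 19% at 0.10. That is the extreme case. If the third sample falls at random between periods, it adds noise rather than a consistent direction.

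**3. What non-rejection means.** Power to detect a true doubling at equal exposure, level 0.10:

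| Events per 34 treatments | Proportions | Power |
|---|---|---|
| 0.1 vs 0.2 | 9.5% vs 18.1% | 13% |
| 0.2 vs 0.4 | 18.1% vs 33.0% | 26% |
| 0.5 vs 1.0 | 39.3% vs 63.2% | 49% |
| 1.0 vs 2.0 | 63.2% vs 86.5% | 56% |

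For very common events (95% vs 99.8%, also a doubled rate) power is 1.4%, because almost every subject has an event in both periods.

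When all discordant subjects fall on one side, five are needed to reject. For 4 vs 0, the corrected statistic is (4 − 1)² / 4 = 2.25, p = 0.134 (exact p = 0.125). For 5 vs 0, exact p = 0.0625.

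**4. What an interval adds.** With n12 subjects having an event only when Assisted and n21 only when Unassisted, d = (n21 − n12)/30 and SE = √[n12 + n21 − (n21 − n12)²/30] / 30. The paired Wald 90% CI is d ± 1.645 SE.

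| n12, n21 | Difference (points) | 90% CI | Exact p |
|---|---|---|---|
| 4, 4 | 0 | −15.5 to +15.5 | 1.0 |
| 2, 5 | +10.0 | −4.2 to +24.2 | 0.45 |
| 3, 8 | +16.7 | −0.8 to +34.2 | 0.23 |
| 0, 4 | +13.3 | +3.1 to +23.5 | 0.125 |

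All four are non-rejections, with upper limits between 15 and 34 points. In the last row the Wald interval excludes zero although the test does not reject, so the interval method must be chosen to match the test.

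**The case against.** A reader might infer that unequal exposure will routinely distort these comparisons because training keeps subjects longer in the Assisted period and Device Holidays lengthen either one. The documents do not support that. Section 7.1.4 says "Subjects may exit the Assisted Evaluable Period before training is complete if all required treatments have been performed", and section 3.3 places further training in Transition Period B. Section 9.7.1 allows an extension so that the required number of treatments is reached, which brings counts back towards 34, although it does add calendar days. Overrun is not excluded, since no maximum is set, but completers should be near balance.

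It is also fair that both periods share one laboratory schedule, that 9.5 gives counts and breakdowns by system organ class, preferred term and severity as well as tests, and that the primary model adjusts all AEs for treatments. Nothing in the plan says that non-rejection will be taken as equal safety. Section 9.8 refers further AE analyses to the SAP; the text available contains none, so intervals or adjusted rates may already be planned there. Overdispersed events would weaken the exposure effects shown above.

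What stands is narrower: early leavers, unequal sample numbers, low power, and no interval or population stated in 9.5.

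**Conclusion.** The point holds in limited form. For completers, exposure imbalance is likely to be small and its effect on the AE tests tolerable. For early leavers, the at-least-one comparison favours the Unassisted period and can hide a real excess. For the laboratory endpoints, 2 against 3 samples alone moves the expected proportion from 36% to 49% at an assumed 20% per sample. With 30 pairs, power for a doubled rate is about 13 to 56% over the assumed range of 0.1 to 1.0 events per 34 treatments, and close to nil for very common events, so a non-significant result cannot reassure by itself. All of these sizes rest on assumed rates and independence. It remains a change worth making, because the categories named as central to the safety judgement have no adjusted rate or interval in the section that compares them.

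**What to change.** In section 9.5:

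- **(a) AE rates.** For each of the six categories, report events per 100 treatments in each period and the rate ratio with a 90% CI on the ITT population, using the offset already specified in 9.4.1, beside the subject counts. State how subjects with little or no Unassisted exposure enter the paired table.
- **(b) Paired differences.** Report the paired difference in proportions with a 90% CI by a named paired method that agrees with the McNemar version used. Section 9.5 calls the test exact but writes a chi-square rule, so that version must be settled first. State that non-rejection is not evidence of no difference.
- **(c) Laboratory incidences.** Base the phosphorus and potassium comparisons on the same number of scheduled monthly samples in each period, with all values still listed.

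Do not restrict the AE comparison to subjects with 34 treatments in both periods, except as a labelled sensitivity analysis. That would condition a safety comparison on completion and drop those who left because of AEs, a reason for discontinuation listed in section 5.3.

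Cost: wording and some programming, with no new data or subjects. Ratios for rare categories will be imprecise, and cannot be estimated usefully where one period has no event. Some extra laboratory values will fall outside the comparison.

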4.2.2 Secondary Endpoints

- 1. Number of anticipated and unanticipated AEs and SAEs during each Evaluable Period including number of device-related AEs and SAEs.
- Incidences of decreased and increased post-dialysis serum phosphorus during each Evaluable Period.
- Incidences of decreased and increased post-dialysis serum potassium during each Evaluable Period.
- 4. A descriptive summary of UF and target weight during each Evaluable Period.

5 Study Population

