8.1.7 Adverse Events Related to Hemodialysis Therapy (Anticipated Adverse Events)

The following are common adverse reactions (signs, symptoms and diagnoses) that have been reported related to HD therapy: hypotension; hypertension; muscle cramps; nausea; vomiting; headache; chest pain; back pain; itching; fever; chills; disequilibrium syndrome; hypersensitivity (allergic) reactions including asthmatic reactions, respiratory arrest, pruritus, urticaria, erythema, and peripheral and facial edema; hypovolemia; hypervolemia; cardiac arrhythmia; cardiac tamponade; intracranial bleeding; seizures; hemolysis; air embolism including micro-air embolism; blood loss; infection; access related problems including infiltration; abdominal pain; fluid overload; hematuria; bleeding; and electrolyte imbalance. Definitions of these adverse reactions are provided in Appendix 1.

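### Secondary endpoint 1 counts AEs by category, but section 9.5 item 1 tests only whether each subject had at least one, which discards repeat events and has low power for common categories

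*Combined protocol and SAP*

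**What the plan says.** Section 4.2.2 defines the first secondary endpoint as a count: "Number of anticipated and unanticipated AEs and SAEs during each Evaluable Period including number of device-related AEs and SAEs". The matching objective in section 4.1.2 is worded as a descriptive comparison: "To compare descriptively all reported adverse events (AE) and serious adverse events (SAE; anticipated, unanticipated, and device-related".

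Section 9.5 item 1 handles this endpoint in two ways. It tabulates: "An overview of the total number of AEs and SAEs (anticipated, unanticipated, and device-related) during each Evaluable Period will be provided", with further summaries by SOC and PT. It also tests: "The proportion of subjects having at least one AE within each of these six AE subgroups will be compared between Evaluable Periods". The six subgroups are anticipated, unanticipated and device-related events, each for AEs and SAEs. The test is McNemar, two-sided, with this rule: "The Null Hypothesis will be rejected if the P-value for the x^2 is less than 0.10". On multiplicity: "No multiplicity adjustment will be done for these secondary endpoints". No rate ratio or interval is planned for any subgroup.

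Section 8.1.7 defines anticipated AEs by a broad list of reactions that it describes as common in hemodialysis, beginning "hypotension; hypertension; muscle cramps; nausea; vomiting; headache". Section 9.4.1, the primary safety analysis, does compare AE counts between the periods. It uses a negative binomial rate ratio with a 90% CI and log number of treatments as offset, but only for all AEs together.

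**The concern.** McNemar uses only discordant subjects, those with an event in one period and none in the other. A subject who goes from two hypotension episodes to twelve is concordant and carries the same weight as one with no change. The more common a category is, the more subjects are concordant, so the test weakens exactly where repeat events hold most of the information. Section 8 requires every AE to be recorded however often it recurs in a subject, so the counts will be available and this test will not use them.

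At stake is how any increase by type of event would be judged once the medical professional is no longer present. Section 9.2 rests the clinical safety determination on both the rate and the type of AEs. By type, the plan offers raw totals and a yes/no test, and no comparison of rates with a measure of uncertainty.

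**Working it through.** **Plan's own figure.** Section 9.2 expects 30 subjects with 34 treatments per period: 30 × 34 = 1,020, which meets its goal of at least 1,000. The documents give no power, AE rate or effect size for the secondary AE comparison.

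**Inputs.** From the documents: 30 paired subjects, 34 treatments per period, two-sided 0.10. Assumed: a true doubling; AE rates of 1 to 20 per 100 treatments in the Assisted period; equal exposure; Poisson counts with a shared gamma subject effect of mean 1 and variance v from 0 to 2.

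**How many discordant subjects are needed.** With 20 or fewer discordant pairs, section 9.5 uses Q = (|n12 − n21| − 1)² / (n12 + n21). If all discordance runs one way:
- 4 versus 0: Q = 9/4 = 2.25, p = 0.134, not rejected.
- 5 versus 0: Q = 16/5 = 3.2, p = 0.074, rejected.

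So at least 5 discordant subjects are required even in the cleanest case.

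**How many are expected.** With mean m events in a period, P(none) = (1 + v·m)^(−1/v), or exp(−m) when v = 0. P(none in either period) uses the sum of the two means. For v = 0.5:
- 10 per 100: means 3.4 and 6.8. P(none) = 2.7⁻² = 0.137 and 4.4⁻² = 0.052; none in either = 6.1⁻² = 0.027. Expected discordant = 30 × (0.137 + 0.052 − 2 × 0.027) ≈ 4.0. Positive in both = 1 − 0.137 − 0.052 + 0.027 ≈ 84%.
- 3 per 100: means 1.02 and 2.04. P(none) = 1.51⁻² = 0.439 and 2.02⁻² = 0.245; none in either = 2.53⁻² = 0.156. Expected discordant = 30 × (0.439 + 0.245 − 2 × 0.156) ≈ 11.1. Positive in both ≈ 47%.

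**Power for a doubling.** 20,000 simulated trials per setting. McNemar follows the section 9.5 rule. The count comparison is ln(S_u/S_a), where S_u and S_a are total events in the Unassisted and Assisted periods (the offset cancels with equal exposure). Its subject-clustered SE is √[n/(n−1) · Σ(y_u/S_u − y_a/S_a)²]. Ranges are over v = 0, 0.5, 1 and 2.

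| AEs per 100 (Assisted) | Positive in both periods | McNemar | Count rate ratio |
|---|---|---|---|
| 1 | 14-15% | 21-40% | 58-60% |
| 3 | 36-56% | 25-55% | 92-94% |
| 5 | 46-79% | 23-40% | 99% |
| 10 | 60-96% | 0.3-17% | 100% |
| 20 | 71-99.9% | 0-10% | 100% |

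Section 9.5 names the exact test but prints chi-square formulas; the two gave practically the same power.

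**Extra period-to-period variation.** With subject variance 0.5-1 and an independent period-level variance of 0-0.5, McNemar gives about 22-43% at 1-5 per 100 and 1-19% at 10-20. The count ratio gives about 47-57% at 1, 68-99% at 3-5 and 81-100% at 10-20.

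**Size.** With no true difference, the count ratio rejected in about 9-14% of trials. McNemar, at v = 0.5 without period variation and 1-10 per 100, rejected in 2.5-5.3%. The comparison is therefore not size-matched and somewhat flatters the count method, but the gap at 3 per 100 and above is too large to be explained by that.

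**What the primary analysis would show.** If anticipated AEs at rate a double and other AEs at rate o do not change, the total-AE ratio is (2a + o)/(a + o). For a = o = 5 it is 15/10 = 1.5; for a = 20, o = 10 it is 50/30 ≈ 1.67. The 90% CI for the total ratio, computed with the same clustered method, lay above 1 in about 54-98% of trials for a/o from 3/3 to 20/10 per 100.

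**The case against.** The strongest reply is that the plan already compares counts. Section 9.4.1 models total AEs per treatment, anticipated events enter that total directly, and a doubling confined to them would often move the primary rate ratio. This stands. A reader might infer that nothing in the plan could pick up a doubling, and the documents do not support that. What remains is that the total is diluted by other events, does not say which category rose, and is judged against a margin δ to which section 9.4.1 gives no value.

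Second, the objective is descriptive and category totals are tabulated, so a doubling would be visible. This also stands, and the McNemar tests add to the tables rather than replace them. But raw totals carry no uncertainty and are not divided by the number of treatments. A rate ratio with an interval serves a descriptive aim better than six unadjusted p-values.

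Third, one might infer that nearly every subject will be positive in both periods. That needs roughly 8-10 or more anticipated AEs per 100 treatments and little variation between subjects, and the documents state no rate. At 3 per 100 only 36-56% are positive in both.

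Fourth, the simulated count method is not the section 9.4.1 model. That model has an unstructured subject effect for period with only two records per subject, and the section itself plans for non-convergence. This is fair, and the fix uses a simpler subject effect.

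Fifth, where events are rare, as SAE categories may be, McNemar loses less, so the point bears mainly on anticipated AEs. Finally, section 9.8 refers further AE analyses to the SAP. If a per-category rate comparison is specified there, the point is already met; none appears in the text available.

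**Conclusion.** The point holds in limited form. For secondary endpoint 1, the count is tabulated but the only test is of at-least-one, and no per-category rate comparison with uncertainty is planned. Against a doubling, the planned test is at best about a coin flip (roughly 20-55% power at 1-5 AEs per 100 treatments) and weak at 10 or more (under about 20%). A count-based ratio on the same data reaches about 47-60% at 1, 68-99% at 3-5 and 81-100% at 10 or more. These figures assume 30 subjects with equal exposure and the stated range of subject and period variation; the AE rates are assumptions throughout.

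Low power for common categories is the supported conclusion. That a doubling would go undetected is not: McNemar itself finds it in a minority to about half of trials at lower rates, and the primary analysis and the tables offer other routes. The primary safety conclusion is unaffected. This is a worthwhile, inexpensive improvement to a secondary analysis.

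**What to change.** In section 9.5 item 1, for each category with enough events (at minimum anticipated AEs), add the Unassisted/Assisted rate ratio with a 90% CI. Obtain it from a paired count model with log number of treatments as offset and a simple subject effect, either a random intercept or subject-clustered standard errors. Use the overdispersed Poisson fallback of section 9.4.1 if the model does not converge. State in advance the number of events below which the model will not be fitted.

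Keep the at-least-one proportions as descriptive figures and McNemar for sparse categories. Add a sentence that a non-significant McNemar result in a common category is not evidence of no increase.

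The cost is a little SAP wording and some reuse of the primary analysis code on data already collected. Intervals will be wide in categories with few events, and because the clustered method ran slightly above nominal size at 30 subjects, a small-sample correction is worth considering.

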- Number of anticipated and unanticipated AEs and SAEs during each Evaluable Period including number of devicerelated AEs and SAEs.
- 2. Incidences of decreased and increased post-dialysis serum phosphorus during each Evaluable Period.
- Incidences of decreased and increased post-dialysis serum potassium during each Evaluable Period.
- 4. A descriptive summary of UF and target weight during each Evaluable Period.

Exploratory Endpoints:

- Reliability of HemoCare™ Hemodialysis System for the provision of treatments as scheduled and the ability to deliver prescribed treatments.
- Proportion of subjects and care partners who successfully complete training with HemoCare™ Hemodialysis System and enter the Unassisted Home Evaluable Period.
- 3. Subjects' scores for Patient Recovery Time Questionnaire, Renal Treatment Satisfaction Questionnaire (RTSQ) and Care Partner scores for Zarit Burden Interview 12 item version (ZBI-12).

	4. A descriptive summary by Evaluable Period of the total number of alarms, type of alarms and the time to resolve alarms will be provided.
Study Population:	Up to 70 subjects receiving HD may be enrolled in this study in order to achieve approximately 30 subjects entering the Unassisted Home Evaluable Period. No more than 25% of the total study subjects who complete the study may be enrolled at one site.
Study Duration:	Duration of Study participation will be documented by the Subject's active participation which is expected to be a minimum of 34 treatments per Evaluable Period.
Study Design and Methodology:	This is a prospective, multi-center, open-label, single-arm, cross-over study.
	A written informed consent will be obtained from each subject and care partner before starting any study related procedures. Subjects will undergo screening for eligibility during which inclusion and exclusion criteria will be evaluated. The screening period will be up to 30 days prior to enrollment.
	Eligible subjects will enter In-Facility Introduction Period during which they will begin training at the study site. This period will last approximately 1 to 6 weeks, but may be extended up to 12 weeks at the Investigator's discretion. The subjects will receive professionally attended Hemodialysis (HD) treatment with HemoCare TM Hemodialysis System at least 3 times every seven days. The duration of each HD treatment will be determined by the clinician on a case by case basis.

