9.2 Determination of Sample Size

The goal is to have at least 1000 HemoCare™ treatments in both Evaluable Periods, in agreement with the FDA, to make a *clinical determination* of the safety of HemoCare™ based on the rate and type (i.e., device related) of AEs documented. To achieve this goal, at least 30 subjects will enter the Assisted Evaluable Period. No more than 25% of the total study subjects who complete the study may be enrolled at one site. Assuming each Evaluable Period is 3.5 treatments per week (one treatment every other night), each patient is expected to contribute 34 treatments to each Evaluable Period and 68 evaluable treatments to the study.

Based upon the number of treatments and the expected rate of adverse events, the current study design is under-powered to detect a clinically meaningful (less than 10%) non-inferiority margin for the Unassisted Evaluable Period.

For the primary performance endpoint, 'success' is defined as a subject who has all stdKt/Vurea measures in an evaluable period greater than or equal to 2.0. Several sets of simulation samples were generated (2,000 samples per set) assuming a rate of success between 95% and 99.5% for the Assisted Evaluable Period treatments paired with some fewer successes for the Unassisted Evaluable Period treatments. The success rate of the 2 periods were compared and the CI interval for the differences were calculated. With 30 subjects in each Evaluable Period, a margin of 10% will provide 91% power to declare non-inferiority if the actual success rate is 99% and 83% power if the actual success rate is 98%.

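### For the six adverse-event subgroup comparisons, Section 9.5 names exact McNemar tests but states a chi-square rule that is not exact, is undefined with no discordant pairs, and can exceed its 10% level above 20 discordant pairs (minor, secondary endpoints)

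*Combined protocol and SAP*

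**What the plan says.** Section 9.5, item 1, takes six subgroups (anticipated, unanticipated and device-related AEs, and the same three for SAEs). For each, the proportion of subjects with at least one event "will be compared between Evaluable Periods with exact McNemar's tests". The hypotheses are two-sided.

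The same item then defines the decision. With n12 and n21 the two discordant counts, Q = (n12 − n21)²/(n12 + n21) is referred to chi-square "with 1 Degree of Freedom if" n12 + n21 exceeds 20. Otherwise Q = (|n12 − n21| − 1)²/(n12 + n21) is used. "The Null Hypothesis will be rejected if the P-value for the" chi-square "is less than 0.10". There is no multiplicity adjustment, and nothing is said about n12 + n21 = 0.

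Items 2 and 3 of Section 9.5 cover low and high post-dialysis phosphorus and potassium. These four incidences "will each be compared between Evaluable Periods with exact McNemar's tests", with no formula and no level of their own. Section 9.1 sets a default for the whole plan: unless otherwise specified, "treatment effects will be evaluated based on a 2-sided significance level of 0.050".

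**The concern.** An exact McNemar test is a two-sided binomial test on the discordant pairs. Neither Q formula is that test, so two programmers working from the same item could report different p-values and, at some splits, different decisions.

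Two consequences need sizing. First, both formulas divide by the number of discordant pairs, so the rule gives no answer when there are none. Three of the six subgroups are SAE categories, where that outcome is plausible. Second, the continuity correction is dropped above 20 discordant pairs, so the rule may reject more often than its stated 10%.

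At stake is what gets called a difference between periods in secondary safety tables that carry unadjusted p-values. The primary analyses are not affected.

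**Working it through.** **Inputs.** From Section 9.5: the two Q formulas, the switch at 20 pairs, and rejection at p < 0.10, i.e. Q > 2.7055 (chi-square, 1 df). From the Protocol Summary and Section 9.2: about 30 subjects with data in both periods. The documents give no discordance rate, so every value of ψ (the probability that a subject is discordant) below is an assumption. The plan states no achieved size for these tests; the only figure to check against is the nominal 0.10.

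**Step 1: no discordant pairs.** The corrected formula gives (|0 − 0| − 1)²/0 = 1/0. The probability of this with 30 subjects is (1 − ψ)³⁰:

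| Assumed ψ | P(no discordant pairs) |
|---|---|
| 1% | 0.99³⁰ = 74% |
| 2% | 0.98³⁰ = 55% |
| 5% | 0.95³⁰ = 21% |
| 10% | 0.90³⁰ = 4% |

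The exact test gives p = 1 here.

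**Step 2: size given the number of discordant pairs.** Under the null hypothesis, n12 given n = n12 + n21 is Binomial(n, 0.5). Conditional size is the total probability of the splits that the rule rejects.

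- For every n from 1 to 20, the corrected formula and the exact test reject the same splits. The largest size is 9.6%, at n = 18.
- For n from 21 to 30, they differ at four counts:

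| n | Split where they differ | Q | Chi-square p | Exact p | Size, written rule | Size, exact test |
|---|---|---|---|---|---|---|
| 22 | 7/15 | 8²/22 = 2.909 | 0.088 | 0.134 | 13.4% | 5.2% |
| 25 | 8/17 | 9²/25 = 3.240 | 0.072 | 0.108 | 10.8% | 4.3% |
| 27 | 9/18 | 9²/27 = 3.000 | 0.083 | 0.122 | 12.2% | 5.2% |
| 29 | 10/19 | 9²/29 = 2.793 | 0.095 | 0.136 | 13.6% | 6.1% |

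The dropped correction is the cause. At 7/15 the corrected Q would be 7²/22 = 2.227, below 2.7055, and the null would stand. For all n up to 70, the written rule peaks at 13.6% (n = 29) and the exact test at 9.9% (n = 37).

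**Step 3: how likely that region is.** With p the event probability in each period under the null, ψ = 2p(1 − p) − 2cov. If the within-subject covariance is not negative, ψ is at most 0.5. Overall size averages the conditional sizes over n ~ Binomial(N, ψ). At ψ = 0.5:

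| Pairs N | P(more than 20 discordant) | Overall size, written rule |
|---|---|---|
| 30 | 2.1% | 6.1% |
| 35 | 16% | 6.8% |
| 40 | 44% | 7.7% |
| 50 | 90% | 9.3% |
| 70 | over 99.9% | 10.0% |

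The exact test at 30 pairs and ψ = 0.5 also has overall size 6.1%. With 30 pairs the written rule passes 10% overall only at very high discordance: 10.2% at ψ = 0.9 and at most 11.2%, at ψ = 0.97.

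**The case against.** The strongest reply is that the mismatch hardly affects a decision. It is largely right about error rates. The 13.6% is conditional on exactly 29 discordant pairs, almost every subject in a study of about 30. A reader might take it as the error rate of these tests; Step 3 shows that it is not.

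A reader might also combine "at least 30 subjects will enter the Assisted Evaluable Period" with "Up to 70 subjects receiving HD may be enrolled in this study" and conclude that 40, 50 or more pairs are to be expected. The Protocol Summary does not support that. It ties the 70 enrolled to roughly 30 entering the Unassisted Home Evaluable Period, and a McNemar pair needs data from both periods. Nor does a common category imply many discordant pairs: if most subjects have an anticipated AE in each period, those pairs are concordant.

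A reader might extend the Q rule to all ten comparisons and cite raised potassium as a case of 1/0. The formulas and the 0.10 level stand only under item 1, so the documents do not state that rule for the laboratory comparisons.

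The stakes are low. The first secondary objective (Section 4.1.2) is a descriptive comparison, no success criterion rests on these p-values, and with no discordant pairs no difference could be claimed anyway. Section 9.1 also leaves further detail to the SAP.

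What remains is that the named test and the stated rule conflict within one item, and that the rule has no value in a plausible case. Neither depends on sample size.

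**Conclusion.** The point holds as a minor error in a secondary analysis. For the six AE subgroups the plan names one test and prescribes another. The prescribed rule is undefined with no discordant pairs, which is the likelier practical failure: 21% to 74% with 30 subjects for assumed discordance of 5% down to 1%. Above 20 discordant pairs its conditional size exceeds 10% at 22, 25, 27 and 29 pairs, and it rejects at splits where the exact test does not.

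At the planned 30 or so pairs the documents do not support a claim of materially inflated error: the overall size is about 6% at 50% discordance. That rests on non-negative within-subject correlation and on roughly 30 subjects contributing to both periods. For the four laboratory comparisons the only gap is the level: the text does not say whether 0.10 or the 0.050 default of Section 9.1 applies.

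**What to change.** In Section 9.5, item 1, delete both Q formulas and the switch at 20 pairs. Define the test as the two-sided exact binomial p-value on (n12, n21), with p = 1 when n12 + n21 = 0. In items 2 and 3, keep the exact test already named and state whether 0.10 or 0.050 applies.

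The cost is a wording change. Standard software provides the exact test, and no extra data or subjects are needed. The p-values become slightly more conservative, and no decision changes where there are 1 to 20 discordant pairs. A confidence interval for the paired difference would be a useful but optional addition.
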